5. STUDY DESIGN

This is a Phase 3, Randomized Control Trial, Multi centre, Single-blind, and Parallel group of 6 ± 1 days duration of data collection after topical application to compare the efficacy and safety of standard treatment of musculoskeletal pain in adult populations.

Justification :

- Phase 3 (Confirmatory study)
The study is conducted to demonstrate whether or not a product offers a treatment benefit to adult participants with musculoskeletal pain between test drug (Piroxicam plus Counterirritant) and commonly used NSAID topical products, Piroxicam gel, Diclofenac gel
- Randomized Control Trial (RCT)
Participants are randomly assigned to different treatment or control groups to minimize bias and allow for causal inference.
- Multi centre
The study will be conducted in 2 sites
- Single-blind
To keep this study maintain the integrity of the data, the investigational product will be given a white sticker to cover all over the tube of investigational products. On top of the tube, there is a study label with unique code to differentiate the test drug and comparator drug. With this procedure, participants will not know which products that assigned to them. Therefore participants can be blinded.
- Parallel

The study in which two groups of participants receive Piroxicam plus Counterirritant gel or Piroxicam gel, or Diclofenac gel. Participants are assigned to one of the treatment arms at the beginning of the trial and continue in that arm throughout the length of the trial. Assignment to a group usually is randomized.

5.1 Primary End-Point:

The primary end-point is the difference of musculoskeletal pain reduction ≥ 3 scores, of the response to treatment that can be seen through Brief Pain Inventory (BPI) scores.

Justification:

- The Brief Pain Inventory (BPI) scores.

It is a medical questionnaire that is used to assess pain. It has also been validated for pain assessment chronicle. There are 9 questions related to the pain experienced by the participants. The pain assessment will be given in the form of a score, namely a score of 0 - 10.

Score 0 : No Pain

Score 1 – 3 : Mild Pain

Score 4 – 6 : Moderate Pain

Score 7 – 10 : Severe Pain

The difference BPI scale ≥ 3 , from initial scale of pain to the end of treatment will be captured as the primary efficacy endpoint.

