6.1 Target Populations

Participants who were diagnosed with acute musculoskeletal pain will be recruited in this study.

The acute musculoskeletal pain caused by arthritis such as osteoarthritis (OA) with Grade 0 until III Kellgren-Lawrence (KL) grading, or musculoskeletal disorders such as ankle sprain, patella tendinitis, tennis elbow, and back pain as mentioned in topical NSAIDs indication that approved by BPOM RI.

Diagnosis criteria were made by history taking, physical examination and radiologic evaluation if necessary.

Justification:

Acute musculoskeletal pain is defined as pain arising from the musculoskeletal system (muscles, bones, joints, ligaments, and tendons) that is sudden in onset and relatively short-lived.

- Subject with musculoskeletal pain caused by Osteoarthritis, Grade 0 – Grade III Kellgren-Lawrence
 - Grade 0 : No radiographic evidence of osteoarthritis.
 - Grade 1 (Doubtful) : Possible osteophytes (bone spurs) and doubtful joint space narrowing.
 - Grade 2 (Minimal) : Definite osteophytes and possible joint space narrowing.
 - Grade 3 (Moderate) : Moderate joint space narrowing, multiple osteophytes, some sclerosis (increased bone density), and possible bone deformity.
- Subject with musculoskeletal pain caused by musculoskeletal disorder, such as :
 - Ankle sprain is a common injury that occurs when the ligaments in the ankle are stretched or torn due to a sudden twisting or rolling motion of the foot.
 - Patellar tendinitis, also known as jumper's knee, is an inflammation of the patellar tendon, which connects the kneecap (patella) to the shinbone (tibia).
 - Tennis elbow, also known as lateral epicondylitis, is a condition characterized by pain on the outer side of the elbow, specifically near the bony prominence (lateral epicondyle). It's typically caused by overuse or repetitive motions of the forearm muscles, which can lead to tiny tears and inflammation in the tendons that attach these muscles to the elbow.
 - Back pain, also known as dorsalgia, refers to pain experienced in the back, from the base of the neck to the top of the buttocks.

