6.6 Subject Enrollment

A unique subject IDs will be assigned to each participant by the Investigator at 1st visit. This number will serve as the participant's identifier in the study as well in the study database. This subject IDs will be unique across each site and it will be a 5 digit number including last three digits will be the subject ID at each site with hyphen between the site number and the last three digits. Site number will be assigned by Sponsor.

At the start of the study, the principal investigator assigns participant ID to the participants who gave written consent by themselves. Two copies of the screening list of participants that includes the information of the participants who gave consent are prepared. One copy is retained and the other copy is submitted to the sponsor. Regarding the participants who were not enrolled, the reason is recorded.

On the CRFs or other documents submitted to the Sponsor, participants should not be identified by their names, but by their assigned subject IDs only. If subject names are included on copies of documents submitted to the Sponsor, the names must be obliterated and the assigned subject ID added to each of the documents.

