6.12 Dispensing, Storage, Management, and Collection Procedures

The Study Drug Handling Manual will be provided and completed to ensure the study drugs are prepared, shipped, stored, dispensed, and returned to comply with regulations.

The Investigational Products will be relabelled in Sponsor Technical Operations Plant Site. After the Sponsor ensures the quality of the product, the study drug will be relabeled, which means that this drug is used explicitly for clinical studies.

The sponsor will deliver the study drug from the Technical Operations plant to each research site by courier, where it can monitor the temperature of the study drug delivery below 30°C.

The Study Coordinator from each research site will ensure the storage of study drugs.

During the study, the distribution of study drug participants will be prescribed by the Investigator based on randomization and dispensed to the participants by the Sports Therapist during the recovery program.

Use GraphPad QuickCalcs (<https://www.graphpad.com/quickcalcs/randomize1/>) to generate a random allocation list, ensuring equal numbers for each treatment group:

- Group A: Piroxicam + Counterirritant
- Group B: Piroxicam
- Group C: Diclofenac

Each eligible participant will be assigned a unique subject ID upon enrollment. The study coordinator will match the subject ID to a treatment group based on the pre-generated list. All tubes will be labeled with a sticker displaying only the randomization code to maintain blinding of both participants and investigators. The tube will then be dispensed to the participant according to the assigned code. Only the investigator will have access to the full randomization list.

At the end of the study period, all study drugs will be returned by the participants to each site. This return process will be assisted by each Study Coordinator. An then be sent to Technical Operations for destruction.

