7.7.2 Study period and process

The study period for each participant is defined as “the period from the day of consent to the end of study (the day on which final tests and observation are finished or the day of discontinuation of the study).

The participants considered as a complete visit after the 3rd visit examination on 6 ± 1 days visit.

[figure not shown]
- 1st visit consider as Day 0
- 2nd visit is on Day 3 ± 1 days
- 3rd visit is on Day 6 ± 1 days

The study's flow in Day 0 :

- 1) The registration officers will receive participants who register at the Eminence clinic and ask about symptoms related to the participant's visit. If the Participant complains of pain, the patient will be asked to fill out a registration form.
- 2) The Principal Investigator or Sub Investigator will ask some questions (anamnesis) about the symptoms and explain about a clinical study that is conducted in the clinic. The PI or Sub-I will ask the Participant's willingness to join the research and explain regarding informed consent. If the Participant agrees, an informed consent will be signed.
- 3) The participants are asked to complete the Individual Assesment of Pain.
 - a. Form 2 : Pemeriksaan Inventerisasi Rasa Nyeri Singkat
- 4) The examination was carried out by conducting anamnesis, physical examination to confirmation the musculoskeletal pain, range of motion and muscle test and confirmation related to the inclusion and exclusion criteria. If needed a radiologic examination will be conducted.
- 5) In the examination, the PI or Sub-I should complete some Forms :
 - a. Form 3 : Pemeriksaan Awal Rasa Nyeri
 - b. Form 4 : Pemeriksaan Indikator Rasa Nyeri Non Verbal
 - c. Form 5 : Pemeriksaan Rentang Gerak
 - d. Form 6 : Pemeriksaan Kekuatan Otot
- 6) The PI or Sub-I will provide a diagnosis and therapy appropriate to the diagnosis.

- 7) Randomization of participants is carried out helped by Study Coordinator. The administration of therapeutic drugs according to the randomization list by a physiotherapist. The physiotherapist will provide information related to how to apply topical drugs to participants and provide the first dose of the investigational product in the therapy room.
 - a. Form 7: Pemberian aplikasi obat topikal by Physiotherapist
 - b. Form 8: Sensasi Termal by Participant
- 8) Each participant will get physical therapy program referred to standard protocol and diagnosis

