7.4.2 Statistical Analysis Plan

The statistical analysis will be performed after data finalization and database lock, following the predefined analysis sets (PPS, FAS, and Safety Analysis Set). All analyses will be conducted using standard statistical software (e.g., SPSS, SAS, or R), with the level of statistical significance set at $p < 0.05$, unless otherwise adjusted.

Efficacy Analysis

- **Primary Endpoint (Pain Score using Brief Pain Inventory):**
 - **Test: Analysis of Covariance (ANCOVA)** adjusting for baseline BPI score

- **Equivalence testing:** Pairwise comparisons using **two one-sided t-tests (TOST)** to assess whether the difference in mean change from baseline falls within the equivalence margin (± 1.0)
- **Assumptions:** Normality and homogeneity of variance will be checked. If violated, non-parametric equivalent (e.g., **Wilcoxon rank-sum test**) will be used.
- **Secondary Endpoints:**
 - **Range of Motion (ROM) and Muscle Strength:**
 - **Test:** Repeated Measures ANOVA or mixed-effects model, depending on data completeness and correlation structure
 - If non-normal: **Friedman test** or **Wilcoxon signed-rank test** for within-group, **Kruskal-Wallis test** for between-group comparisons.
 - **Thermal Sensation, Comfort, and Acceptance (ASHRAE Scale):**
 - **Test:** Chi-square test or Fisher's exact test for categorical comparisons
 - **Ordinal regression** may be used to explore patterns of thermal perception across groups.
 - **Responding Analysis (pain reduction ≥ 3 points):**
 - **Test:** Chi-square test for group-wise comparison of response rates
 - **Risk difference** and **number needed to treat (NNT)** will be calculated.

Safety Analysis

- **Adverse Events (AEs) and Adverse Drug Reactions (ADRs):**
 - **Test:** Chi-square test or Fisher's exact test for comparing incidence across groups
 - Descriptive statistics for type, severity, onset, and duration
 - **Severity grading** and **causality assessment** using **Naranjo's algorithm**.
- **Rescue Medication Use:**
 - **Test:** Poisson regression or negative binomial regression if data are overdispersed
 - Summarized as a mean number of doses used per participant and compared between groups.

Demographic and Baseline Characteristics

- **Continuous Variables** (e.g., age, BMI):
 - **Test:** One-way ANOVA or **Kruskal-Wallis test** (if non-normal distribution)
- **Categorical Variables** (e.g., sex, diagnosis):
 - **Test:** Chi-square test or Fisher's exact test as appropriate

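### The primary ANCOVA adjusts for baseline BPI only and should also pre-specify diagnosis group and site: a valid analysis that gives up precision in an equivalence test against ±1.0

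*Protocol*

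**What the plan says.** **Allocation.** Section 6.12 describes one list generated in advance with an online tool, "ensuring equal numbers for each treatment group". It adds that "The study coordinator will match the subject ID to a treatment group based on the pre-generated list". No block size or stratification factor appears there or elsewhere in the protocol.

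**Primary model.** Section 7.4.2 specifies an ANCOVA, "adjusting for baseline BPI score". It lists pairwise TOST at ±1.0 as a separate item and does not say that the TOST contrasts come from the ANCOVA.

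**Diagnosis.** Section 6.1 admits "The acute musculoskeletal pain caused by arthritis such as osteoarthritis (OA) with Grade 0 until III Kellgren-Lawrence (KL) grading", and also ankle sprain, patellar tendinitis, tennis elbow and back pain. Section 7.7.2 states: "Each participant will get physical therapy program referred to standard protocol and diagnosis". In the same Day 0 flow, the diagnosis is made before randomisation. Section 7.4.2 already lists diagnosis among the categorical baseline variables.

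**Site.** Section 5 says: "The study will be conducted in 2 sites". Section 6.6 builds the site into the subject ID, "with hyphen between the site number and the last three digits".

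**The concern.** Equivalence is claimed only if the whole interval for a pairwise difference lies within ±1.0. Any avoidable width in that interval, or chance shift in its centre, counts directly against the claim.

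Diagnosis is the obvious source of both. Section 2.2 says that a sprained ankle or muscle pull usually improves in two to three weeks untreated. It says nothing similar of osteoarthritis, which is enrolled up to grade III. Different six-day courses are therefore a reasonable inference, though the protocol does not document them. Appendix 2 adds a second route. Massage, TENS and ultrasound are common to all five diagnoses, but the exercises differ. An arm with more of one diagnosis thus also receives more of that diagnosis's exercise programme.

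Both diagnosis and site are known at Day 0, so using them in the model needs no extra data collection. Naming them now also avoids choosing covariates after the baseline table has shown an imbalance.

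**Working it through.** **Inputs.** From section 6.7: SD 1.81, margin 1.0, power 80%, α 0.05 or 0.05/3 = 0.0167, 54 evaluable and 60 enrolled per arm. The variance explained by diagnosis and site (R²) is not in the documents, so a range of 5–20% is assumed. The SD of 1.81 is taken as the residual SD after baseline BPI, which is also an assumption.

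**The plan's own figure.** The printed formula gives ((2.39 + 0.84) × 1.81 / 1.0)² = (3.23 × 1.81)² = 34.2, not 54. The next line of the protocol puts 4.059 where 3.23 should stand, and (4.059 × 1.81)² = 54.0. The dropout step does reproduce: 162 / 0.9 = 180. The sample-size error is a separate matter; 54 is used below only as the planned evaluable number.

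**Step 1: chance imbalance without stratification.** For a diagnosis with prevalence p and two arms of 60, the 95% range of the difference in proportions is ±1.96 × √(2p(1−p)/60):

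| p | 95% range (percentage points) |
|---|---|
| 0.2 | ±14.3 |
| 0.3 | ±16.4 |
| 0.4 | ±17.5 |

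Simulation of 20,000 unstratified 60/60/60 allocations, with five equally common diagnoses assumed, gave these probabilities:

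| Imbalance | One named diagnosis, one pair of arms | Some diagnosis, some pair |
|---|---|---|
| ≥10 points | 21% | 90% |
| ≥15 points | 5% | 46% |

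**Step 2: effect on the estimate.** A 15-point imbalance in a factor worth an assumed 1–2 BPI points shifts the difference by 0.15 × 1 = 0.15 to 0.15 × 2 = 0.30.

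The assumed gap must agree with the assumed R². A gap d at prevalence p implies R² = d²p(1−p)/1.81², where 1.81² = 3.28. For d = 1 and p = 0.2–0.4 this is 0.16/3.28 to 0.24/3.28, or 5–7%. For d = 2 it is 0.64/3.28 to 0.96/3.28, or 20–29%. A 2-point gap therefore sits at or above the top of the 5–20% range. Worked directly from R², the 95% extreme shift is 1.96 × √(2/60) × 1.81 × √R² = 0.648 × √R². That is 0.14 at R² = 0.05 and 0.29 at R² = 0.20.

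**Step 3: effect on power.** Under a true difference of zero, with the normal approximation:

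SE = 1.81 × √(1−R²) × √(2/54); power = 2Φ(1.0/SE − z₁₋α) − 1, with z = 1.645 (α 0.05) or 2.128 (α 0.0167).

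At R² = 0, SE = 0.348 and 1.0/SE = 2.87. Power is then 2Φ(1.226) − 1 = 78.0% at α 0.05, and 2Φ(0.743) − 1 = 54.2% at α 0.0167.

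| R² | Power, α 0.05 | Power, α 0.0167 | n per arm for 80% at 0.0167 |
|---|---|---|---|
| 0 | 78.0% | 54.2% | 77 |
| 0.05 | 80.7% | 58.6% | 73 |
| 0.10 | 83.3% | 63.1% | 69 |
| 0.20 | 88.2% | 72.1% | 61 |
| 0.30 | 92.6% | 80.8% | 54 |

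**Step 4: cost.** With 162 evaluable participants, the present model has 162 − 4 = 158 residual degrees of freedom. Four more parameters for a five-level diagnosis factor and one for site leave 153.

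**The case against.** The strongest reply is that nothing here is an error. Simple randomisation with a baseline-adjusted ANCOVA is a valid design. Imbalance in diagnosis is random, and the standard error already allows for it. The shift in Step 2 and the loss of power in Step 3 are thus two views of one source of variance and should not be added together. All of this stands.

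The power figures are also open to challenge. Section 6.7 takes 1.81 from a trial in acute trauma-induced pain. Nothing shows that it contains variance between osteoarthritis and sprain, or that it is a residual after baseline. This stands too, so the figures are illustrations only. If 1.81 excludes that variance, the unadjusted SD in this mixed population exceeds 1.81. Adjustment would then bring power back towards about 78% or 54% from a lower start. The direction of the gain does not change.

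Four stronger readings might be inferred, and the documents support none of them:

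- **Site drives physiotherapy or prognosis.** Section 7.7.2 and Appendix 2 tie the programme to diagnosis, with no variation by site, and the protocol nowhere calls site prognostic. The sample labels in section 6.9 place both sites under one clinic group. Site belongs in the model by convention.
- **The list is known to be unstratified.** This is read from silence. Section 6.6 says the "last three digits will be the subject ID at each site", which would be compatible with a list per site, though none is described.
- **The covariates are left to a later plan.** Section 7.4.2 names the covariate itself, so the point can be raised on the protocol.
- **The list must be stratified by diagnosis.** Sections 6.6 and 6.12 match subject IDs to one list, so stratifying would need separate lists and a new matching procedure. Tube numbers show the arm letters C, H and P (section 6.9), so small blocks within small strata would make the next allocation easier to guess. Two collapsed groups would also not balance five exercise programmes.

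**Conclusion.** The point holds as a worthwhile, nearly free improvement, not as the correction of an invalid analysis. Section 7.4.2 omits two recorded baseline factors from the primary model. For one of them, diagnosis, the protocol itself gives grounds to expect an influence on short-term pain.

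The size rests on an assumed R² of 5–20% and a residual SD of 1.81. On those terms power per pair rises by about 3–10 percentage points at one-sided 0.05, and by about 4–18 points at 0.0167. The corresponding 95% extreme chance shift is 0.14–0.29 against the margin of 1.0.

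A reader might infer that the adjustment rescues the trial's power. It does not: at the Bonferroni level 80% is reached at 54 per arm only if R² is about 0.3. The remaining shortfall belongs to the sample-size calculation. Nor do the documents support a claim of bias, because the imbalance is not systematic.

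**What to change.** In section 7.4.2, pre-specify the primary ANCOVA with treatment, baseline BPI, diagnosis group and site. State that the three pairwise TOST confidence intervals come from that model. Under the one-sided 0.05 level these are 90% intervals; under 0.0167 they are 100 − 2 × 1.67 = 96.7% intervals. Define the diagnosis groups now, with a rule for merging sparse ones. The five headings of Appendix 2 are the natural starting point.

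The cost is a line or two of text and about five degrees of freedom, with no new data. The change can be made after enrolment has begun, provided it is fixed before database lock.

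If enrolment has not begun, the list in section 6.12 could also be stratified by site, and the site-numbered IDs would suit that. This is optional, and stratification by diagnosis group is not required.

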Range of motion (ROM) or motion arc in this study will be measured using a universal goniometer following standardized procedures to ensure accuracy and reproducibility. Each joint will be assessed in a consistent anatomical position—either supine, seated, or standing—depending on the specific joint involved (e.g., seated for elbow, supine for knee). The Principal Investigator or Sub-Investigator will perform three consecutive measurements for each motion (e.g., flexion, extension), and the average value will be recorded. Key movements assessed will include knee flexion-extension, ankle dorsiflexion-plantarflexion, elbow flexion-extension, and lumbar spine flexion or fingertip-to-floor distance for back pain. The same assessor will conduct all measurements at each time point to minimize inter-rater variability. Any limitations due to pain, guarding, or compensatory movements will be noted. ROM data will be recorded on standardized forms and used to evaluate treatment effectiveness by comparing baseline to post-treatment values against established minimal clinically important difference (MCID) thresholds.

In this study, the minimal clinically important difference (MCID) for joint range of motion (ROM) will be used to define clinically meaningful improvements in mobility following treatment. Based on validated references, the MCID values applied are $\geq 10^\circ$ for knee flexion/extension (Mizner et al., 2005) and elbow flexion-extension arc (Picha et al., 2020), $\geq 5^\circ$ for ankle dorsiflexion/plantarflexion (Cleland et al., 2013), and either $\geq 10\%$ change or ≥ 5 cm improvement for lumbar spine mobility, depending on the measurement method used (Stratford et al., 1994). These thresholds represent the minimum degree of change perceived as beneficial by patients and are appropriate benchmarks for evaluating functional recovery in musculoskeletal pain conditions.

- 3) Assessment to investigate scales on thermal sensation, thermal comfort, and thermal acceptance using ASHRAE 7-point scale questionnaire and completed with time starting the thermal sensation.

Definition:

Thermal comfort is the condition of mind that expresses satisfaction with the thermal environment and is assessed by subjective evaluation.

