6.9 Study Drugs Labelling

A label is needed for the study drug used.

Investigational products will be given to Participants in tube only, no individual box.

All Investigational Products tubes will be covered by white sticker, leaving only the tip of the tube containing the batch number and expiration date information. On top of the white sticker will be a study drug label that have specific code and number.

Below is the labelling process for investigational products :

The packaging label from investigational products will be covered by a white secured sticker. Only the bottom side (tail) which contains the batch number information is left open.

Clinical study label will be put on the top of white sticker.

PRODUK INVESTIGASIONAL NO. BATCH : 4M3101 TGL KADALUARSA : Dec 27 NO. REG : DTL1124403528A1 PENYIMPANAN : Simpan dibawah suhu 30° C <small>Dibuat oleh : PT. Taisho Pharmaceutical Indonesia, Tbk</small>	NO. OBAT : C001 NAMA SITE : Klinik Utama Eminence
PRODUK INVESTIGASIONAL NO. BATCH : 4M3101 TGL KADALUARSA : Dec 27 NO. REG : DTL1124403528A1 PENYIMPANAN : Simpan dibawah suhu 30° C <small>Dibuat oleh : PT. Taisho Pharmaceutical Indonesia, Tbk</small>	NO. OBAT : C199 NAMA SITE : St. Carolus Sports Clinic by Eminence

Final label on the tube

Every tube will be numbered with drug number sequentially, as detailed:

Test drug (Yellow sticker)	Comparator drug (Orange Sticker)	Comparator drug (Brown Sticker)
C001	H001	P001
C002	H002	P002
C003	H003	P003
etc. until the last of stock	etc. until the last of stock	etc. until the last of stock

- Initial “C” for study drug and 3 digits number
- Initial “H” for comparator drug and 3 digits number
- Initial “P” for comparator drug and 3 digits number

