7 STUDY PLAN

7.7.1 Group Composition

The following 2 groups are examined. The participants are allocated to these groups at the ratio of 1:1 that will be randomized.

[figure not shown]
- Test drug group : Piroxicam plus Counterirritant Gel
- Comparator group : Diclofenac diethylamine Gel
- Comparator group : Piroxicam Gel

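### The randomisation list is held by the investigator who enrols and assesses, so allocation is not concealed and the stated investigator blinding fails; arm-coded tubes make participant blinding unreliable.

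*Protocol*

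**What the plan says.** Section 5 calls the trial single-blind. It describes a white sticker over each tube with a study label on top, and concludes: "With this procedure, participants will not know which products that assigned to them". The same paragraph says the code on that label serves to tell test drug from comparator.

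Section 6.12 goes further: "All tubes will be labeled with a sticker displaying only the randomization code to maintain blinding of both participants and investigators". Just before this, it says: "The study coordinator will match the subject ID to a treatment group based on the pre-generated list". It ends the paragraph with: "Only the investigator will have access to the full randomization list".

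Section 6.9 numbers the tubes C001, C002 and so on for the test drug, and H001 and P001 onward for the comparators. The three series carry yellow, orange and brown stickers respectively. The two sample labels shown, both for C tubes, print batch number, expiry, registration number and manufacturer as well as the drug number and site.

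**The concern.** Concealment and blinding are separate safeguards, and both are in question.

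- **Concealment** protects the comparison before assignment. If the person deciding whether and when a patient enters can see the next arm, the groups may differ at baseline in ways that adjusting for the baseline pain score does not remove. No analysis can restore concealment afterwards.
- **Blinding** protects what follows: how participants score pain, how doctors measure motion and strength, who is advised to use rescue medication, and who is withdrawn. The primary pain score is self-reported (Form 2), and the primary analysis set is the Per Protocol Set (section 7.4.1). Decisions on compliance and withdrawal therefore bear on who is analysed.

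**Working it through.** The protocol gives no figure on this point, so the check compares its statements.

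**1. What the list-holding role does.**

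| Task | Role | Section |
|---|---|---|
| Explains the study, obtains consent | Principal or sub-investigator | 7.7.2, Day 0 |
| Confirms eligibility, with a discretionary exclusion | Investigator | 6.3, 7.7.2, 7.9 |
| Assigns the subject ID at visit 1 | Investigator | 6.6 |
| Holds the full list | Investigator | 6.12 |
| Prescribes by randomisation | Investigator | 6.12 |
| Measures motion and strength | Principal or sub-investigator | 5.2, 7.7.2 |
| Assesses causality of adverse events | Investigator | 5.2 |
| Sets rescue dosage; may reduce or stop study drug | Investigator | 6.10, 6.13 |

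On measurement, section 5.2 is explicit: "The Principal Investigator or Sub-Investigator will perform three consecutive measurements for each motion". Nothing in the protocol separates the investigator who holds the list from the one who enrols or measures.

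**2. Concealment.** The list exists before enrolment, and treatment follows from matching the subject ID to it. The same role assigns the ID and can read the list. With three equal groups, someone without the list would guess the next arm correctly about 1 time in 3. Someone who reads the list before taking consent knows it with certainty. Concealment is therefore not secured as written.

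**3. Who is blinded.** Section 5 blinds participants. Section 6.12 claims to blind investigators too, then gives them the list. These statements cannot all hold. The claim that only the investigator has the list also conflicts with the coordinator's task of matching IDs to groups from it.

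**4. What the label shows.** Section 6.12 says the sticker displays nothing but the randomisation code. Section 6.9 adds a letter and a colour that are constant within an arm, and its sample C labels add a registration number and manufacturer. C, H and P are the first letters of the brands in sections 6.8.1 to 6.8.3 (Counterpain PXM, Hotin DCL, Pirofel). Anyone with the protocol can read the arm from the tube. The topical application form in Appendix 1 records the tube number, so the letter also enters the study records.

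**5. Reach of the code.** Section 6.7 plans 60 participants per arm, and 3 × 60 = 180. Because the letter is fixed by arm, decoding one letter identifies 60 participants. Decoding two leaves the third by elimination, and so identifies all 180.

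**6. A clash of letters.** In section 6.12, Group C is diclofenac. In section 6.9, a C tube is the test drug. With a coordinator translating groups into tubes, this invites dispensing errors.

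**The case against.** The strongest defence is that the trial is declared single-blind. An investigator who knows the arm after assignment, and who then measures motion or judges causality, is a limitation of a chosen design rather than a contradiction of it. The primary endpoint is completed by the patient, so assessor knowledge reaches it only indirectly. The schedule in section 7.9 gives randomisation to the coordinator, and section 7.7.2 places it after the examination. A Study Drugs Handling Manual that is not shown may say more.

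Much of this stands for the period after assignment. It does not excuse access to the list before enrolment, nor the sentence claiming that investigators are blinded. The later step performed by the coordinator does not conceal a list that the investigator already holds. A stricter manual would contradict section 6.12 as written.

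A reader might infer three stronger things that the documents do not support:

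- **That participants are not blinded at all.** A white sticker covers the pack, no box is given, and each participant normally sees one letter and one colour. Decoding it requires knowledge of the brand names, and nothing shown says participants are told them. The registration and manufacturer cue is shown only for C labels.
- **That the bias could match the ±1.0 equivalence margin.** No passage gives a basis for its size or direction.
- **That one list serves both sites.** Section 6.12 does not say whether the list is prepared per site.

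It is also fair that better labels cannot fully blind participants. Section 2.1 reports a warm feeling after application of the combination product, and thermal sensation is itself a secondary endpoint.

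**Conclusion.** The point holds and should be settled before enrolment. As written, allocation is not concealed from those who enrol, and the investigator blinding claimed in section 6.12 does not exist. Participant blinding is weakened and cannot be relied on.

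The defect is structural. The arm code applies to every tube for all 180 planned participants, and the assessments made by investigators are directly exposed. The self-reported primary endpoint is exposed through selection at enrolment, weak participant masking, and decisions on rescue medication and withdrawal. The size of any bias is unknown.

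The conclusion assumes that the investigator in section 6.12 is the same role as the investigator who enrols and examines, since the protocol draws no distinction.

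Section 7.7.1 speaks of two groups ("The participants are allocated to these groups at the ratio of 1:1 that will be randomized") above a list of three. That needs its own correction and is not part of this argument.

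**What to change.** 1. **List custody.** Have the randomisation list and the kit-to-product key prepared and held by someone outside enrolment and assessment, for example at the sponsor's plant, which already relabels the tubes. Remove list access from the investigator and the coordinator. Release only the next kit number to the site, after consent and eligibility are confirmed.
2. **Labels.** Replace the arm letters and colours with one scrambled kit sequence on labels of identical format, with no text that identifies the arm. Check the exposed tail of the tube, where batch and expiry show, for the same problem. Keep sealed code-breaks for emergencies.
3. **Text.** State one level of blinding in sections 5, 6.9 and 6.12. If investigators will know the arm after assignment, delete the claim that they are blinded. Either way, concealment before assignment must stand.
4. **Reporting.** Acknowledge in the study report that the warm sensation may unmask some participants whatever the labels show.

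The cost is a new label run, a kit list, dispensing by kit number, and a named custodian outside the enrolling team. No visits are added.
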